**Noninvasive Ventilation for Preterm Neonates With
Respiratory Distress Syndrome: a Multi-center Randomized
Controlled Trial**

(NCT03099694)

13 July 2017

Solid PDF/A Express
<http://www.SolidDocuments.com/>

STUDY PROTOCOL

Noninvasive high-frequency oscillatory ventilation versus nasal continuous positive airway pressure in preterm infants with respiratory distress syndrome: Study protocol for a multi-center, prospective, randomized, controlled trial. For the Noninvasive High-Frequency Oscillatory Ventilation Study Group (NHFOV Study Group*).

Abstract

Background: Invasive mechanical ventilation is associated with development of adverse pulmonary and non-pulmonary outcomes in very low birth weight infants. Various modes of non-invasive respiratory support are being increasingly used to decrease the incidence of bronchopulmonary dysplasia (BPD). The aim of this trial is to compare the effect of noninvasive high-frequency oscillatory ventilation (NHFOV) and nasal continuous positive airway pressure (NCPAP) in preterm infants with respiratory distress syndrome (RDS) as a primary noninvasive ventilation support mode.

Methods/Design: In this multicenter, randomized, controlled trial, 300 preterm infants born at gestational age (GA) less than 34 weeks with a diagnosis of RDS will be randomized to NHFOV or NCPAP as a primary mode of noninvasive respiratory support. Study will be conducted in 18 tertiary neonatal intensive care units in China. The primary outcome is the need for invasive mechanical ventilation (IMV) during the first 7 days after enrollment in preterm infants randomized to the two groups. The

prespecified secondary outcomes include days of hospitalization, days on noninvasive respiratory support, days on IMV, days on supplemental oxygen, mortality, need for surfactant, severe retinopathy of prematurity(ROP) requiring laser or surgery, patent ductus arteriosus needing ligation, bronchopulmonary dysplasia(BPD), occurrence of abdominal distention, air leaksyndromes, intraventricular hemorrhage (IVH \geq grade 3), necrotizing enterocolitis (NEC \geq II stage) and nasal trauma. Other secondary outcomes include Bayley Scales of Infant Development at 18-24 months of corrected age.

Trial registration: ClinicalTrials.gov Identifier: NCT03099694.

Key words: Noninvasive high-frequency oscillatory ventilation; nasal continuous positive airway pressure; respiratory distress syndrome; preterm infants; surfactant; invasive mechanical ventilation

Background

Respiratory distress syndrome (RDS) due to surfactant deficiency is the leading cause of respiratory failure in preterm infants [1]. Early noninvasive positive pressure ventilation has become a recommended strategy for respiratory management of preterm infants with RDS [2]. In addition to nasal continuous positive airway pressure (NCPAP), various types of noninvasive ventilation (NIV) modes have been used in the treatment of RDS including heated, humidified, high-flow nasal cannula (HHFNC), biphasic NCPAP (BP-NCPAP) and nasal intermittent positive airway pressure (NIPPV) [3]. However, clinical trials have shown that 25 to 67% of very low birth weight preterm infants fail these NIV modes and require IMV [4-5]. To minimize the need of IMV, noninvasive high-frequency oscillatory ventilation (NHFOV) has been studied as a rescue treatment after failure of other NIV modes or following extubation from IMV during weaning phase [6]. However, to date, no studies have been published on the efficacy of NHFOV as a primary mode of respiratory support in preterm infants. In the present trial, we aim to compare the effect of NHFOV and NCPAP in preterm infants with RDS as a primary NIV mode. Our main hypothesis is that NHFOV is more effective in the treatment of preterm infants with RDS than NCPAP when used as a primary NIV mode.

Trial Design

Aim

The primary aim of this trial is to compare the need for IMV during the first 7 days of life in infants randomized to NHFOV versus NCPAP.

Study design

This will be a multi-center, prospective, randomized controlled trial conducted in 18 tertiary neonatal intensive care units (NICUs) in China. The trial will be performed in accordance with prospective trial flow (Fig.1).

Inclusion criteria:

(1) Gestational age (GA) is from 26 weeks 0 days (26⁺⁰weeks) to 33 weeks 6 days(33⁺⁰weeks) (estimated on the postmenstrual date and early gestation ultrasonographic findings); (2) diagnosis of RDS. The diagnosis of RDS will be based on clinical manifestations(tachypnea, nasal flaring and or grunting) and the typical X-ray picture of RDS (grain shadow, air bronchogram or white lung)-see appendix; (3) RDS Silverman score>5; (4) Age <12 hours; (5) informed parental consent has been obtained.

Exclusion criteria

(1) Resuscitation requiring early intubation according to the American Academy of Pediatrics guidelines for neonatal resuscitation [8]; (2)major congenital malformations or known complex congenital heart disease; (3)pulmonary hemorrhage or pneumothorax; (4) congenital lung diseases or malformations or pulmonary hypoplasia;

Setting

We plan to enroll preterm infants born between 26 and 34 weeks of gestational age from 18 tertiary NICUs in China. These 18 tertiary NICUs have more than 800 NICU beds and annual admissions of nearly 8,000 preterm infants with RDS each year. The first (XZ) and last authors (RR) take responsibility for the accuracy and completeness

of the trial.

Randomization

To avoid the chance of having more infants in one group than another, block randomization will be applied, with a block size of 4. The envelopes are sealed, shuffled, and then numbered in sequential order from 1 to 4. A clinician who is not in the trial group will open the envelope and randomize patients. This procedure will be repeated for each group of four infants. Infants will be stratified according to 26^{0/7}-27^{6/7} weeks, 28^{0/7}-29^{6/7} weeks, 30^{0/7}-31^{6/7} weeks and 32^{0/7}-33^{6/7} weeks. Infants born from multiple gestations will be assigned by individual randomization. Infants randomized to one arm cannot crossover to the other or vice-versa during the study.

Trial intervention

Ventilators

CPAP: CPAP will be provided by continuous flow devices (CNO Medin, Germany or Carefusion, USA) Bubble CPAP devices will not be used.

NHFOV: NHFOV will be provided by two ventilators (CNO, Medin, Germany or SLE 5000, UK). The Medin CNC ventilator produces high-frequency oscillations by flow interruption with cyclic opening-closure of the end expiratory valve. Otherwise, The SLE 5000 ventilator is a time-cycled, pressure-limited and continuous-flow neonatal ventilator.

Before the beginning of the study all ventilators will be checked to ensure that there is no malfunction.

Interfaces

CPAP and NHFOV will be all administered through short, low-resistance binasal prongs,

since these are supposed to be the best in terms of resistive charge, leaks and/of comfort. Nasal prongs size will be chosen according to the nares' diameter as the best fitting ones (the largest ones that fit the nares without blanching the surrounding tissues) and following manufacturer's recommendations. Particular care (e.g.: pacifiers, positioning, nursing) will be applied to reduce leaks and improve patients' comfort. These matters will be evaluated through a dedicated 30 min observation period when study intervention will be instigated.

Ventilatory management

The two different respiratory supports will be managed as follows:

CPAP: Neonates assigned to the CPAP group were initiated on a pressure of 5 cmH₂O. CPAP can be raised in steps of 1 cmH₂O up to 10 cmH₂O. If this is not enough to maintain target oxygen saturation (SpO₂) from 89% to 92% in preterm infants <30 weeks GA and 90-94% in infants ≥30 weeks GA by pulse oximeter, FiO₂ will be added up to 0.40.

NHFOV: For Medin CNO, the initial NHFOV settings will be: mean airway pressure (MAP) of 6cmH₂O (range 6-10cmH₂O), frequency of 10 Hz (range 6-12), The Medin CNO has ten grades of amplitude. grade 7th amplitude will be to start with (grade range 7th-10th). For SLE 5000, The initial settings will be: MAP of 6 cm H₂O (range 6-10cmH₂O); frequency of 10Hz (range 6-12), inspiratory time 50% (1:1), oscillations of amplitude of 20 cm H₂O (range 20-35 cm H₂O). It is not strictly necessary to have visible chest oscillations, as most of the CO₂ elimination during NHFOV will occur in the upper airway dead space. Maximal allowed FiO₂ will be 0.40 and SpO₂ from 89% to 93% in

preterm infants <30 weeks GA and 90-94% in infants \geq 30 weeks GA by pulse oximeter.

Surfactant Therapy

Surfactant (Poractant alfa, Chiesi Pharmaceuticals, Parma, Italy) at dose of 200 mg/kg will be administered via INSURE method if infant presents with the following: infants \leq 26 week's gestation when FiO_2 requirement >0.30 and infants >26 week's gestation when FiO_2 requirement >0.40 [2]. Additional doses of surfactant may be given using INSURE technique at the discretion of the clinician.

Caffeine Therapy

Caffeine (Caffeine Citrate Injection, Chiesi Pharmaceuticals, Parma, Italy) will be administered when infants present with moderate apnea (defined as 3 or more episodes in 24 hours or a single episode requiring resuscitation and bag-mask ventilation). The initial loading dose is 20mg/kg, and the maintenance dose is 5mg/kg per day.

Weaning from study interventions

The criteria for weaning noninvasive respiratory will be: (1) minimal or no signs of respiratory distress (RDS Silverman score < 5) ; (2) NHFOV MAP or NCPAP pressure <6 cmH₂O and (3) $FiO_2 < 0.25$ to achieve target SpO₂.

Criteria for intubation and IMV

These will be as follows [10-11]: (1)severe respiratory acidosis ($P_aCO_2 > 65$ mmHg with $pH < 7.20$);(2)severe apnea and bradycardia (defined as recurrent apnea with >3 episodes per hour associated with heart rate < 100 /min, a single episode of apnea that

requires bag and mask ventilation); (3) hypoxia ($FiO_2 > 0.5$ with $PaO_2 < 50$ mmHg), severe respiratory distress (RDS Silverman score > 7); (4) pulmonary hemorrhage; (5) pneumothorax; (6) cardiopulmonary arrest needing chest compressions.

Training

Since not all clinicians are well versed in all respiratory techniques and, particularly, NHFOV is a relatively new technique, the training is capital for the trial success. The protocol will be diffused between participating centers at least 3 months before the study begins. One investigator (YS) will explain the study protocol in an in-person meeting with all investigators. During the two months' period, clinicians will familiarize with the protocol and the respiratory techniques and the two co-principal investigators will be available to solve any doubt. A dedicated social media chat has been set to facilitate these exchanges. The trial is supposed to actually start in July 2017.

Outcomes

The primary outcome of this trial will be to determine the need for IMV in the first 7 days of life in preterm infants randomized to the two groups. Secondary outcomes include days of hospitalization, days on noninvasive ventilation, days on supplemental oxygen, pre-discharge mortality, surfactant doses, incidence of stage III ROP and BPD, occurrences of abdominal distention, air leaks, IVH \geq grade 3 and NEC. Secondary outcomes also include Bayley Scales of Infant Development at 18-24 months of corrected age. BPD will be defined according to the National Institutes of Health consensus definition as mild, moderate and severe BPD [12], IVH classification according to Papile et al [13] and for NEC, Bell staging will be used [14].

Data collection

Patient demographic data include: sex, birth weight, gestational age, Apgar scores, mode of

delivery, prenatal corticosteroid use, premature rupture of the membrane, RDS Silverman score and critical risk index for babies-II (CRIB-II) score. More details see in the appendix Clinical data :Including the need for IMV, days of hospitalization, days on noninvasive respiratory support, days on supplemental oxygen, mortality, the need for surfactant, occurrences of abdominal distention, air leaks, IVH \geq grade and NEC \geq stage II. More details see in the appendix Follow-up data: The incidence of BPD and ROP at a post-menstrual age of 36 weeks or at discharge, and Bayley Scales of Infant Development at 18-24 months of corrected age.

Sample size calculation

It is difficult to calculate a sample size for such a study, since it is the first to investigate NHFOV vs CPAP in primary support phase in preterm infants with RDS. There is only one preliminary study available about the primary outcome “need for IMV”. This pilot study conducted by Zhu et al provides data about the primary outcome “need for IMV”. This trial showed the need for IMV was significantly lower in the NHFOV compared with the NCPAP group (24.3% vs. 56.4%, $P < 0.01$). Considering an α -error of 0.05 and a power of 90%, 150 neonates should be enrolled in each arm (with a 1:1 design) to detect the same difference.

Statistical methods

Data will be analyzed using SPSS version 19 software. The statistical analyses include Student's t-test for continuous data and compared proportions using Chi-squared test, and Fisher's exact test for categorical data. Predefined four subgroups are 26^{0/7}-27^{6/7} weeks, 28^{0/7}-29^{6/7} weeks, 30^{0/7}-31^{6/7} weeks and 32^{0/7}-33^{6/7} weeks, and subgroup analyses will be conducted for the primary outcome in the preterm infants. To further evaluate the effect of NHFOV on intubation within

subgroup, the test of treatment-by-gestational age subgroup interaction will also be done using the paired binary logistic regression. For the preterm infants lost to follow-up, the missing values of the primary and secondary outcomes are replaced using multiple imputation. A P -value < 0.05 will be regarded as statistically significant.

Data Safety Monitoring Board (DSMB): [name], Professor of Pediatrics, Oklahoma University Medical Center, Oklahoma, [name], Professor of Pediatrics, Medical College of Georgia, Georgia Health Sciences University, Augusta, Georgia, and [name], MD., MPH (Biostatistics and Epidemiology) Assistant Professor of Pediatrics, Keck School of Medicine of the University of Southern California, Los Angeles, California will serve as DSMB members. [name] will also serve as consultant for statistical analysis.

Registration number

The trial has been approved by the centralized ethics committee (The Ethics Committee of Daping Hospital, Research Institute of Surgery, Third Military Medical University) and registered at <http://www.clinicaltrials.gov>(ID: NCT03099694).

Discussion

In the past decades, several clinical trials have compared the effects between NHFOV and NCPAP in neonates as a rescue mode or during weaning from IMV. These trials demonstrated that NHFOV applied with nasopharyngeal tube are more beneficial than NCPAP in reducing CO₂ levels [16-19]. Recently, two retrospective case series also reported NHFOV could be applied in preterm infants as a rescue treatment after the

failure of other noninvasive ventilation modes[15,20].However, there are some limitations in these trials: 1) small sample size; 2) lack of a prospective, randomized trial design; and 3) wide range of NHFOV parameters used in these trials. Given these limitations, a multi-center, prospective, randomized, controlled trial is necessary for better evaluation of NHFOV as a primary mode of noninvasive support. To our knowledge, this will be the first multi-center prospective randomized controlled trial for evaluation of NHFOV as a primary noninvasive mode in preterm infants with RDS in China or any other part of the world. Our trial may help contribute to establish guidelines for NHFOV in preterm infants with RDS to minimize the need for IMV, and to decrease significant pulmonary and non pulmonary morbidities associated with IMV.

Funding

The trial is initiated and planned by the researchers and funded by Scientific Research Projects unit of Chongqing (Project- cstc2016shms-ztxx13001)

Acknowledgement

The authors would like to thank all families whose infants will participate in this trial, and staff providing patient care in all the participating sites.

Conflict of Interest

None of the authors have declared conflicts of interests to participate in this trial.

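### A fixed, disclosed block of 4 with envelopes numbered 1 to 4 makes up to one third of allocations certain to staff who see the earlier ones, and custody of the lists is not described

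*Combined protocol and SAP*

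**What the plan says.** The Randomization section gives the purpose of blocking as "To avoid the chance of having more infants in one group than another" and sets a single block size: "block randomization will be applied, with a block size of 4". On the mechanics it says "The envelopes are sealed, shuffled, and then numbered in sequential order from 1 to 4", then "This procedure will be repeated for each group of four infants". On who acts, it says "A clinician who is not in the trial group will open the envelope and randomize patients". The only stratification factor is gestational age, in four bands; site is not named as a stratum.

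Other sections bear on the point:

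- **Training:** the protocol, block size included, is sent to all participating centers at least three months before the start.
- **Ventilatory management:** frequency and amplitude are set for NHFOV only.
- **Inclusion criteria:** entry requires a Silverman score above 5, a clinical and X-ray diagnosis of RDS, parental consent, and age under 12 hours.
- **Sample size calculation and Abstract:** allocation is 1:1, with 300 infants at 18 units.

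The documents do not say where the envelopes are kept, whether each site has its own lists, whether the envelopes are opaque, or whether anyone is blinded.

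**The concern.** When the block size is known and each envelope shows its place in the block, a person who remembers the earlier allocations can count which arm is used up. Here nobody has to guess where a block begins, because the numbering restarts at 1. Staff can see the earlier allocations because the ventilator settings differ between the arms.

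The person who opens the envelope is not the only one who matters. The person who screens the infant and approaches the parents decides whether and when the infant enters, and that person can do the counting. Entry leaves room for judgment in the bedside score, the diagnosis and the timing within the first 12 hours. The Background section states a hypothesis in favor of NHFOV. A high Silverman score is also one of the listed criteria for intubation, so severity at entry bears directly on the primary outcome, the need for invasive ventilation in the first 7 days. If infants of different severity were steered toward one arm, the primary comparison would be biased.

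**Working it through.** The plan gives no predictability figure, so there is none to reproduce.

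**Inputs.** Block size 4 (Randomization); 1:1 allocation (Sample size calculation); 300 infants and 18 sites (Abstract); four gestational-age strata (Randomization). A split of two and two within each block is implied by the 1:1 ratio and the stated purpose of blocking. It is not stated.

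**Step 1: a complete block, all earlier allocations seen.** There are 6 equally likely orders of two and two. An allocation is certain once one arm is used up.

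| Position | P(certain) | P(best guess right) |
|---|---|---|
| 1 | 0 | 1/2 |
| 2 | 0 | 2/3 |
| 3 | 1/3 (first two in the same arm: 2 of 6 orders) | 1/3 × 1 + 2/3 × 1/2 = 2/3 |
| 4 | 1 | 1 |

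Certain: (0 + 0 + 1/3 + 1)/4 = (4/3)/4 = 33.3%. Hit rate: (1/2 + 2/3 + 2/3 + 1)/4 = (17/6)/4 = 70.8%.

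**Step 2: incomplete blocks.** A list with n = 4q + r infants has (4/3)q + c certain allocations on average, where c = 1/3 if r = 3 and 0 otherwise. The 300 infants were spread at random, with equal chances, over the lists (4,000 simulated trials). All earlier allocations in a list are taken as seen.

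| Lists | Certain | Hit rate |
|---|---|---|
| 4 (one per stratum) | 32.8% | 70.6% |
| 18 (one per site, ignoring the strata) | 30.8% | 69.7% |
| 72 = 18 × 4 (site by stratum; 300/72 = 4.2 infants each) | 23.2% | 66.3% |

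An assumed uneven 10/20/30/40% split over the gestational-age bands changes the last row only to 23.4% and 66.4%.

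**Step 3: lists common to all 18 sites, each site seeing only its own infants.** Assume that infants come independently from 18 equally active sites and that the envelope number is known. Certainty requires that two earlier infants in the same arm of the block were both at this site, which has probability (1/18)² for a given pair. The expected number of such pairs is 1/3 at position 3 and 1 at position 4. The certain share is (1/18)² × (1/3 + 1)/4 = 1/972 = 0.1%. The hit rate is about 51%: seeing any earlier infant of the block raises it from 1/2 to about 2/3, and the chance of that is 0, 0.056, 0.108 and 0.158 at positions 1 to 4, so 0.5 + (1/6) × (0.056 + 0.108 + 0.158)/4 = 0.513.

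**Step 4: randomly varied blocks.** The observer sees every allocation in the list and knows the set of sizes, but not the boundaries. With sizes 4, 6 and 8 equally likely, an exact updating calculation on simulated lists gives 2.3% certain and a 67.8% hit rate for lists of 75 infants, and 2.6% and 67.0% for lists of 16.

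**The case against.** Four objections carry weight.

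1. **Local custody is not in the text.** A reader might infer that envelopes are held and opened at each hospital, since paper envelopes for infants under 12 hours old at 18 hospitals point that way. The documents say only that someone outside the trial group opens them, and site is not a stratum. The text is also compatible with common lists, for which the certain share is about 0.1%. This objection stands. However, no central release is described either, so the plan cannot claim that protection.

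2. **The outside opener is a safeguard.** It keeps the recruiter from opening an envelope early. It does not stop the recruiter from counting past treatments, so it answers only part of the concern.

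3. **The equipment need not look different.** A reader might infer that different devices always reveal the arm. The Ventilators and Interfaces sections list the Medin device for both arms and the same type of prongs. The mode is still evident from the NHFOV settings, so earlier allocations remain visible to treating staff. That is an inference, because the documents do not describe blinding.

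4. **Varied blocks do only part of the job.** They nearly remove certainty but lower the hit rate by only about 3 points, and a probable guess can also be used to steer. This stands and limits what the main fix achieves.

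**Conclusion.** The concern holds in a limited form. A fixed, disclosed block of 4 with visible block positions makes up to one third of allocations certain to staff who see every earlier allocation in a list. The range that the documents leave open runs from about 0.1% to 33.3%, depending on who holds the lists and who sees the earlier allocations. The figures assume two infants per arm in each block and bedside visibility of the mode.

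A reader might go further and infer that a third of allocations in this trial will be foreseen, or that the primary result will be biased by a definite amount. The documents support neither. One third is the ceiling, and nothing in the plan shows how often staff would act on a guess or how much the risk of steered infants would differ. Nor is it right to say that such bias would be wholly beyond repair. Silverman score, CRIB-II, birth weight and gestational age are collected, so imbalance on them could be seen and partly adjusted for, although no adjusted analysis is planned and unmeasured differences would remain. Selection bias is possible, its size is unknown, and it is cheaper to prevent than to correct.

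**What to change.** Revise the Randomization paragraph to do the following:

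- Replace the hand-shuffled sets of four by a computer-generated list within the four gestational-age strata, with randomly varying block sizes.
- Keep the block sizes in a document that does not go to the sites.
- If envelopes are kept, make them opaque and number them consecutively through each list, so that the number no longer shows the place in a block.
- State who prepares and holds the envelopes, and whether lists are per site or common to all sites.

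With blocks of 4, 6 and 8, this lowers certain allocations from as much as 33.3% to about 2%, and the hit rate from 70.8% to about 68%.

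Where a central telephone or web service already exists, releasing each allocation from lists common to all sites, after the infant is registered, would bring the hit rate close to 50%. This is optional, because round-the-clock release for newborns at 18 units needs resources well beyond a new list.

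The main change costs a regenerated list and one revised paragraph. Its statistical price is a slightly larger chance imbalance within strata.

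### The primary test in this 18-centre trial uses neither centre nor gestational-age band: type I error is not inflated, but some precision may be lost

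*Combined protocol and SAP*

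**What the plan says.** Study design describes a "randomized controlled trial conducted in 18 tertiary neonatal intensive care units (NICUs) in China", and the abstract gives a total of 300 infants. Under Randomization, "block randomization will be applied, with a block size of 4". The text continues "This procedure will be repeated for each group of four infants. Infants will be stratified according to" four gestational-age bands between 26 and 33 completed weeks. Centre is not listed as a stratum, and the section does not say whether each unit holds its own envelope sets or all units draw on shared ones.

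For analysis, Statistical methods "compared proportions using Chi-squared test", with Fisher's exact test also named. The only regression is a logistic model for the treatment-by-gestational-age interaction. No centre term appears anywhere, and the gestational-age bands enter only the subgroup work.

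On equipment, "NHFOV will be provided by two ventilators (CNO, Medin, Germany or SLE 5000, UK"), and two makes are also allowed for CPAP. The protocol does not say how makes are distributed over centres.

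**The concern.** With 300/18 = 16.7 infants per unit on average, differences between units in how readily infants are intubated could form a visible part of the outcome variance. The protocol makes such differences plausible without quantifying them. The Training section concedes uneven experience with the techniques, repeat surfactant is left to the clinician, and one intubation criterion is a bedside severity score.

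The unadjusted test handles that variance poorly under either arrangement of the envelopes:

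- **Sets held per unit.** Arms are nearly balanced within each unit, so unit differences largely cancel from the treatment comparison. The chi-squared standard error still counts them. The test is valid but conservative, and an interval built on that standard error is too wide.
- **Sets shared across units.** Arms can be unbalanced within a unit by chance, so unit differences add noise to the estimate. The chi-squared standard error counts that noise correctly, but an adjusted analysis would remove much of it.

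At stake is efficiency: power if the true effect is smaller than planned, and the width of the confidence interval in any case.

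**Working it through.** **1. The plan's own figure.** The inputs, from Sample size calculation, are IMV rates of 24.3% and 56.4% and "power of 90%, 150 neonates should be enrolled in each arm (with a 1:1 design"). Two-sided alpha is assumed, as sidedness is not stated. The mean rate is p̄ = (0.243 + 0.564)/2 = 0.4035.

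n per arm = [1.960·√(2·0.4035·0.5965) + 1.282·√(0.564·0.436 + 0.243·0.757)]² / 0.321² = 47.

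The stated 150 is not reproduced; a continuity correction gives 54. That is a separate matter. It bears on this point because 150 per arm has more than 99.9% power at the stated rates, so there is ample slack at the planned effect.

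**2. The planned effect on the log-odds scale.** ln(0.243/0.757) − ln(0.564/0.436) = −1.136 − 0.257 = −1.39. The −0.7 used below is an assumption, about half of this. From 56.4% it corresponds to odds of 1.294 × e^(−0.7) = 0.642, a rate of 39.1%.

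**3. Why per-unit sets make the test conservative.** The chi-squared standard error is √(p̄(1 − p̄)·2/150) = √(0.2407·2/150) = 0.057. The total variance p̄(1 − p̄) is the average within-centre variance plus the variance of the centre rates. For an assumed centre log-odds SD of 0.8, the latter is roughly (0.8 × 0.2407)² = 0.037, or 15% of 0.2407. With perfect balance within centres, the true standard error is about 0.057 × √0.85 = 0.052. The simulation below, with incomplete blocks, gave 0.053 against a mean chi-squared standard error of 0.057. Then 1.96 × 0.057/0.053 = 2.11, a two-sided error of about 3.5%.

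**4. Simulated trials.** Settings: 300 infants, 18 unequal centres, blocks of 4, log odds ratio −0.7, and 2,000–3,000 trials per setting. The model is a random centre intercept plus gestational-age bands, fitted as a risk difference with robust standard error. Centre SDs are assumed.

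| Centre SD | Power, per-unit sets: chi-squared / model | Power, shared sets: chi-squared / model | Chi-squared type I error, per-unit sets |
|---|---|---|---|
| 0.5 | 80% / 83% | 81% / 83% | 4.7% |
| 0.8 | 75% / 80% | 74% / 77% | 3.8% |
| 1.1 | 66% / 74% | 67% / 73% | 3.7% |

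With no centre effect, power is 84% for both. The model's type I error is 4.9–5.5%.

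A second set of 1,500 trials per setting put the gain from adjustment at 0–2, 1–2, 4 and 6–8 points at SD 0, 0.5, 0.8 and 1.1. The chi-squared type I error was 4.3–5.8% with gestational-age-only sets and 2.5–4.5% with per-unit sets; the model's was 4.1–5.8%. The simulation error of one power figure here is √(0.75·0.25/1500) = 1.1 points, so the two sets agree.

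**5. Is type I error raised?** In 12,000 null trials per setting with sets by gestational age only, the chi-squared test rejected in 5.0%, 4.5%, 5.0% and 5.0% at centre SD 0, 0.5, 1 and 1.5. The mean null difference was 0.000 to 0.001, so the estimate is unbiased. A centre of about 17 infants had a mean absolute arm imbalance of about 3 (90th percentile 7). This costs precision, not validity.

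**6. At the planned 56.4% versus 24.3%.** Power with the unadjusted test was at least 99.6% at every centre SD tried, up to 1.5.

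**The case against.** The strongest reply is that nothing is invalid. Infants are randomized individually, the stated test holds its level, and at the effect the trial was planned for both analyses are almost certain to succeed. That stands. So does the point that every gain above depends on a centre SD and an effect size that the protocol does not give, and that common intubation criteria, joint training and one type of nasal interface may keep centre differences small.

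Nor does adjustment restore everything. With per-unit sets, chi-squared power falls from 84% with no centre effect to 66% at SD 1.1, a fall of 18 points, and the model recovers 74 − 66 = 8. Much of the rest arises because the odds ratio within centres was held fixed while centre variation grew, which shrinks the risk difference.

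The form of adjustment also matters. Stratifying the test by centre and band makes 18 × 4 = 72 cells of about 300/72 = 4.2 infants. At nominal rates of 40% versus 25% with no centre effect and gestational-age-only sets, that cut power from 76% to 67%. This argues for a random intercept, not against adjustment.

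What the objection does not remove is that the planned effect rests on a single preliminary study. If the true effect is smaller, the lost precision counts, and recovering it needs no extra infants.

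**Conclusion.** The point holds as a cheap gain in precision, not as a flaw in validity. The gain is roughly 1–2, 4 and 6–8 power points at assumed centre SDs of 0.5, 0.8 and 1.1 and an assumed log odds ratio of −0.7. It is about nil without centre differences and immaterial for power at the planned rates, although the interval would still be somewhat narrower if centres differ.

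A reader might infer more than the documents support:

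- **Inflated type I error.** With a common treatment effect it stays near 5% with gestational-age-only sets and falls to about 2.5–4% with per-unit sets at SD 0.8–1.1. Only if the treatment effect itself varies between centres, and inference is to a wider population of centres, does rejection exceed 5% (8.2% and 17% with both the centre and the effect SD at 0.5 and 1). Stratifying by centre and band does not cure that (8.6% and 20%).
- **Devices tied to centres.** The Ventilators section lists makes per arm and says nothing about their distribution.
- **Envelope sets known to be held per unit.** This is not stated, so the conservative case is conditional.
- **An unblinded trial.** This is a fair inference from visibly different supports, but it is not stated and the argument does not need it.

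**What to change.** In Statistical methods, make the primary analysis of IMV a model with treatment, gestational-age band and a random intercept for centre. Report the adjusted risk difference with its 95% CI. Name the link, the standard error and, if the link is not the identity, how the risk difference is obtained. The figures above come from a linear risk-difference model with robust standard error. Keep the chi-squared test as supportive. In Randomization, state whether envelope sets are held per centre or shared.

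The cost is a few sentences, slightly more analysis work and some reliance on a model. No extra infants are needed.

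Two further changes are not recommended. Lists by centre within band would make 72 strata of about four infants; with a fixed block of 4, allocations become easier to predict locally. An effect-by-device comparison is not well defined, because only the Medin device is listed for both arms.
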